16.4.2.2. Clinical Laboratory Results

Clinical laboratory evaluations will include hematology, blood chemistry, and urinalysis. Laboratory data will be summarized using shift tables. Shifts from baseline to high/low status for hematology and blood chemistry parameters, and shifts from baseline to high/positive status for urinalysis will be presented. In addition, the shift from baseline to the maximum postbaseline value and the shift from baseline to the minimum postbaseline status will be presented for each laboratory test by treatment group. Also, summaries of laboratory values categorized based on common toxicity criteria grade will be created. Summary statistics for actual values and change from baseline will also be presented for quantitative laboratory data.

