16.4.2.3. Vital Signs

The analysis of vital signs will focus on clinically relevant abnormalities. The number of subjects evaluated and the number and percentage of subjects with clinically relevant postbaseline abnormalities will be presented by treatment group.

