4.1.1 Analysis Population

- Intent-to-treat (ITT) population:

The ITT population is defined as all randomized subjects who received at least one dose of study treatment (BIIB104 or placebo). Subjects will be in the treatment group to which they were randomized in statistical analyses based on the ITT population.

- Per-protocol (PP) population:

The PP population is defined as all subjects in the ITT population who do not have major protocol deviation(s) that impact efficacy. Exclusion of subjects from the PP population will be determined by the SMT members including but not limited to medical director, clinical pharmacologist and biostatistician. The main reasons for exclusion will be documented.

- Safety population:

The safety population is defined as all randomized subjects who received at least 1 dose of study treatment (BIIB104 or placebo). Subjects will be in the treatment group they received in statistical analyses based on the safety population.

- [REDACTED]

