4.5 Safety Analysis

4.5.1 General considerations

Analysis population

Safety population will be used for safety analyses of adverse events, clinical laboratory data, Columbia Suicide Severity Rating Scale (C-SSRS) data, ECG data and vital signs data.

Safety treatment groups

Different from efficacy analysis, for safety treatment group if a subject who was randomized to a placebo group accidentally received one or more doses of the active treatment during the study, he or she will be classed to low or high dose group based on the dose group of the active treatment received. A listing of these subjects will be provided. Safety treatment groups will be the same as the randomization treatment groups for other subjects (subjects randomized to active treatment groups, and subjects randomized to placebo without any accidental active dose). Safety treatment groups will be used for all the safety analyses unless otherwise specified.

Incidence and incidence proportion

Incidence and incidence proportion will be provided in incidence tables. Incidence is defined as the number of subjects who experienced an event. Incidence proportion is defined as the number of subjects who experienced an event divided by total number of subjects in the analysis population, i.e., percentage. Each subject will be counted only once within each category.

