4.5.3.2 Qualitative analysis

Clinically significant laboratories

Clinically significant laboratory data will be summarized using shift tables where appropriate. For each subject, the lab values in hematology, blood chemistry and urinalysis will be flagged as “low”, “normal”, or “high” relative to the normal ranges of the central laboratory, or as “unknown” if no result is available. The categorical value in urinalysis will be flagged as “positive” (or “high”), “negative” (or “normal”), or “unknown”.

For blood chemistry and serum chemistry, shifts tables from baseline to low/high post-baseline will be presented. Shift to low includes normal to low, high to low, and unknown to low. Shift to high includes normal to high, low to high, and unknown to high. For a subject if a lab is collected multiple times at post baseline, as long as one lab value is low this subject is regarded to have “low” post-baseline for this lab parameter. Similarly, if at least one post-baseline lab value is “high” this subject is regarded to have “high” post-baseline for this lab parameter.

For urinalysis, shifts tables from baseline to high/positive post-baseline will be presented. Shift to high/positive includes low to high/positive, normal/negative to high/positive, or unknown to high/positive.

Markedly abnormal laboratory

Markedly abnormal indicate clinically significant laboratory abnormalities determined by Biogen. For hematology and blood chemistry the number and percentage of subjects with markedly abnormal laboratory post-baseline will be summarized by treatment group from the criteria in Table 7. Shifts tables from baseline to markedly abnormal post-baseline will also be summarized. For a subject if a lab is collected multiple times at post baseline, as long as one lab value is markedly abnormal this subject is counted to be markedly abnormal for this lab parameter.

Subject’s listings will also be presented for all subjects with any markedly abnormal laboratory. In the listings, each subject’s complete history from screening to last study visit for that specific laboratory test meeting the criteria will be listed.

Table 7: Criteria for markedly abnormal laboratory

Parameter name	Unit	Low	High
Hematology			
White blood cells	$\times 10^9$ cells/L	<3.0	>16
Lymphocytes	$\times 10^9$ cells/L	<0.8	>12
Neutrophils	$\times 10^9$ cells/L	<1.5	>13.5
Monocytes	$\times 10^9$ cells/L	N/A	>2.5
Eosinophils	$\times 10^9$ cells/L	N/A	>1.6
Basophils	$\times 10^9$ cells/L	N/A	>1.6

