4.5.4 Vital Signs

Vital sign parameters include temperature, systolic blood pressure, diastolic blood pressure, pulse rate, respiration rate and weight. The descriptive statistics for actual values and change from baseline will be summarized at each visit.

The analysis of vital signs will also focus on the incidence of clinically relevant outliers based on the following criteria. The incidence and percentage of clinically relevant outliers determined by each criterion will be summarized. A listing of subjects with clinically relevant vital signs will be provided.

Table 8: Criteria to determine clinically relevant abnormalities in vital signs

Variable	Low	High
Systolic Blood Pressure	<90 mmHg or > 15 mmHg decrease from baseline	>180 mmHg or > 20 mmHg increase from baseline
Diastolic Blood Pressure	< 50 mmHg or > 15 mmHg decrease from baseline	>105 mmHg or > 15 mmHg increase from baseline
Pulse*	< 50 bpm post-baseline or > 20 bpm decrease from baseline	>120 bpm post-baseline or > 30 bpm increase from baseline
Temperature	>38°C or > 1°C increase from baseline	
Respiration Rate	≤10 breaths/min post-baseline and >10 breaths/min at baseline	≥20 breaths/min post-baseline and <20 breaths/min at baseline

* bpm = beats per minute

Visit windows for by visit summaries

For vital sign by visit summaries, the analysis visit should be defined using window in the table below. If there is more than 1 value in the same analysis visit window for a certain parameter for a subject, the closest record to the target visit day will be used for the by visit analysis. If there are 2 values in the same analysis visit window with the same distance from the target visit day for a certain parameter for a subject, then the record with the later date will be used for the by visit analysis.

Table 9: Visit windows for vital sign

Analysis visit	Target visit day	Analysis visit window
Baseline	1	Most recent non-missing pre-dose value
Week 1	8	[2, 10]
Week 2	15	[11, 21]
Week 4	29	[22, 35]
Week 6	43	[36, 49]
Week 8	57	[50, 63]
Week 10	71	[64, 77]
Week 12	85	[78, EOS]

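### Vital-sign outlier percentages fall under a whole-population denominator in the SAP, which omits the protocol's number evaluated; laboratory abnormality tables have no denominator of their own

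*SAP*

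**What the plan says.** SAP 4.5.1 is the general section for all safety data and names adverse events, laboratory data, C-SSRS, ECG and vital signs. It states that "Incidence and incidence proportion will be provided in incidence tables", then: "Incidence proportion is defined as the number of subjects who experienced an event divided by total number of subjects in the analysis population", and equates this with a percentage. Under SAP 4.1.1 a randomized subject enters the safety population with a single dose; no post-baseline assessment is needed.

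**Vital signs.** Protocol 16.4.2.3: "The number of subjects evaluated and the number and percentage of subjects with clinically relevant postbaseline abnormalities will be presented by treatment group". SAP 4.5.4: "The incidence and percentage of clinically relevant outliers determined by each criterion will be summarized". The SAP sentence does not mention the number evaluated. In Table 8 both respiration criteria carry a baseline condition: above 10 breaths/min for the low criterion, below 20 for the high one.

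**Laboratory.** Protocol 16.4.2.2 says "Laboratory data will be summarized using shift tables" and gives neither a number evaluated nor a denominator. SAP 4.5.3.2 says "the number and percentage of subjects with markedly abnormal laboratory post-baseline will be summarized by treatment group from the criteria in Table 7", and defines shifts so that "Shift to high includes normal to high, low to high, and unknown to high". Liver abnormalities are also to be given as number and percentage. None of these has a stated denominator.

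**Examinations.** SAP 4.5.6, by contrast, gives physical and neurological examinations a separate category for results not done or missing.

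**The concern.** Dividing by everyone dosed suits adverse events, because every dosed subject is under observation for them. It suits measured outcomes less well. A subject who was never measured after baseline, or whose baseline makes the criterion impossible to meet, stays in the denominator and can never enter the numerator. The printed percentage then reads as a rate among subjects who could have shown the abnormality, when it is not.

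Safety and tolerability form a secondary objective, so these tables will be read. HbA1c shows the risk without any assumed rate. Protocol 14.2 schedules it at Screening only, yet SAP 4.5.3 lists it and Table 7 gives it a limit of 6.5% or more for post-baseline reporting. Over the full population, that row would print about 0 of 73 in each arm, unscheduled tests aside. It would look like reassurance although no post-baseline test is planned. A printed number evaluated would show this at once.

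**Working it through.** **Inputs from the documents.** 51 evaluable and 73 randomized per group, 30% drop-out, difference 3.5, SD 7, two-sided alpha 0.1 (Protocol 16.6, SAP 3). The documents give no number evaluated for any safety measure and no share abnormal at baseline, so both are assumptions below.

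**Step 1: the plan's own figures.** A two-sample t-test with 51 per group has power 80.6%, matching the stated 80% or so. 51 / (1 − 0.30) = 72.9, rounded up to 73. Both reproduce. N = 73 is used here only as the size of an arm.

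**Step 2: subjects with no post-baseline value.** With x subjects meeting the criterion, N in the safety population and E evaluated, the SAP rule gives x/N and the evaluated rate is x/E. The relative understatement is 1 − E/N; each unevaluated subject adds 1/73 = 1.4%.

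| E (assumed) | 1 − E/73 | x = 7: x/73 vs x/E | x = 15: x/73 vs x/E |
|---|---|---|---|
| 73 | 0% | 9.6% vs 9.6% | 20.5% vs 20.5% |
| 72 | 1.4% | 9.6% vs 9.7% | 20.5% vs 20.8% |
| 69 | 5.5% | 9.6% vs 10.1% | 20.5% vs 21.7% |
| 66 | 9.6% | 9.6% vs 10.6% | 20.5% vs 22.7% |
| 51 | 30% | 9.6% vs 13.7% | 20.5% vs 29.4% |

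The last row is an outer bound in which every projected drop-out leaves with no post-baseline value. It is not realistic. Protocol Table 4 takes laboratory tests and vital signs from Week 1, and one post-baseline value is enough to be evaluated.

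**Step 3: subjects ruled out by their baseline value.** The formula is the same, with E now the number at risk. This applies to the respiration criteria and, if 4.5.1 is taken as the default, to laboratory shifts.

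| Share already abnormal (assumed) | At risk of 73 | 7 events: of 73 vs at risk | 15 events: of 73 vs at risk |
|---|---|---|---|
| 5% | 69 | 9.6% vs 10.1% | 20.5% vs 21.7% |
| 10% | 66 | 9.6% vs 10.6% | 20.5% vs 22.7% |
| 20% | 58 | 9.6% vs 12.1% | 20.5% vs 25.9% |
| 30% | 51 | 9.6% vs 13.7% | 20.5% vs 29.4% |

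**Step 4: an effect in the other direction.** The shift definition counts a change from unknown to high. A subject who was in fact already high, but has no baseline result, enters the numerator. Shift percentages are therefore not certain to be too low; the net direction depends on how many baselines are unknown.

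**The case against.** The strongest reply is that the definition in 4.5.1 is tied to incidence tables, and the only tables the SAP calls by that name are the adverse-event tables in 4.5.2.1. On that reading the laboratory denominator is open rather than wrong. For laboratory data this stands: the defect is an unstated denominator, with 4.5.1 as the only default. It is weaker for vital signs, where 4.5.4 itself speaks of incidence and percentage.

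The protocol asks only that the number evaluated be shown and never makes it the divisor. That also stands, so the choice of divisor is a recommendation and not a protocol requirement.

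Other readings go further than the documents allow:

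- A reader might infer that every safety percentage uses an unsuitable denominator. Adverse events need no change, and examinations show missing results separately.
- A reader might infer that protocol and SAP conflict on laboratory data too. The protocol mentions the number evaluated for vital signs only.
- A reader might infer that these are the only by-arm figures. SAP 4.5.3.1 and 4.5.4 also give descriptive statistics and change from baseline by visit, and summaries of continuous data include n.
- A reader might infer that an arm with more early losses would look clearly safer. Suppose 2% of one arm and 8% of another have no post-baseline value (assumed) and the true rate is 10% in both. The printed rates are 10% × 0.98 = 9.8% and 10% × 0.92 = 9.2%. The gap of 0.6 points is under half a subject of 73. Early-termination visits and continued follow-up after stopping treatment limit such losses further.

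Baseline abnormality should be similar across randomized arms, so the at-risk effect changes the level of the percentages more than the comparison between arms.

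**Conclusion.** The point holds in limited form. For vital-sign outliers, the SAP's own terms lead to a whole-population percentage and drop a number that the protocol says will be presented. For laboratory shifts, markedly abnormal values and liver abnormalities, the denominator is unstated, and the only rule to fall back on has the same weakness.

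The size is modest. Missing data cost about 1.4% relative per unevaluated subject of 73, and nothing if all are measured. The at-risk effect can be larger, but it rests on a baseline share that the documents do not supply; the 20% behind 9.6% versus 12.1% is an assumption. The documents do not support a claim that percentages will be too low in every table or every arm. This is a minor reporting correction with no bearing on efficacy, power or alpha.

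**What to change.** Keep the 4.5.1 definition and state that it governs the adverse-event tables.

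In 4.5.4 and 4.5.3.2, state that percentages are taken over the number of subjects evaluated, and print that number by arm for each parameter. Define evaluated as having one or more post-baseline values. For shifts, and for criteria with a baseline condition such as respiration rate, also require that the baseline value does not already rule the subject out. Show subjects with unknown baseline on a separate line.

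The cost is one or two sentences and one table column. Some percentages will come out slightly higher. In return the protocol's commitment for vital signs is restored, and rows with no scheduled post-baseline test, such as HbA1c, become visible as such.

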4.5.2 Adverse Events

All AEs will be analysed based on the principle of treatment emergence. A TEAE is defined as an AE that started or worsened between the time of first dose of study treatment and the end of study date (EOS/ET Visit) recorded on the eCRF.

To define treatment emergence for AEs with missing start or stop date or time the following additional criteria will be used:

- if both the start and stop dates for an AE are missing, then this AE is considered treatment emergent;
- if the start date for an AE is missing and the stop date falls after the first dose date, then this AE is considered treatment emergent;
- if the start date for an AE was the same as the first dose date, then that event is considered treatment emergent.

4.5.2.1 Summary of adverse events

Overall TEAE summary table will include the number of subjects with any TEAE, with any TEAE by maximum severity, the number of subjects with any related TEAE, the number of subjects with SAE, the number of subjects with related SAE, the number of subjects with TEAE leading to study drug discontinuation, the number of subjects with TEAE leading to study withdrawal, and the number of deaths.

A subject is counted only once within each category in each table. A subject with more than one TEAE for a preferred term will be counted only once in preferred term. Similarly, a subject who experienced more than one TEAE for a system organ class (SOC) will be counted only once in that SOC category.

The sorting order for AE incidence tables, unless otherwise specified, will be by decreasing frequency order of BIIB104 total column within each category. A subject is counted only once within each category in each table. For the table of TEAEs by system organ class and preferred terms sorted by decreasing frequency presented by treatment group, system organ class will be presented in decreasing frequency order of BIIB104 total column, and within each system organ class, preferred terms will be presented in decreasing frequency order of total column. A subject is counted only once within each system organ class and preferred term.

The following TEAE incidence tables will be presented by treatment group:

- Overall summary of adverse events
- TEAEs by system organ class and preferred term sorted by decreasing frequency
- TEAEs by system organ class and preferred term sorted by alphabetical order
- TEAEs with at least 5% higher in incidence for either low or high dose compared to placebo, by SOC and preferred term
- TEAEs by preferred term with an incidence rate of 5% or more in any treatment group
- SAEs by system organ class and preferred term by decreasing frequency
- SAEs by preferred term

- TEAE by maximum severity by system organ class and preferred term
- TEAEs by maximum severity by preferred term
- Related TEAEs by system organ class and preferred term
- TEAEs that led to discontinuation of study treatment by system organ class and preferred term
- TEAEs that led to withdrawal from study by system organ class and preferred term

The following listings will be provided:

- A listing of subjects experiencing seizure event
- A listing of subjects experiencing TEAEs
- A listing of subjects experiencing SAEs
- A listing of subjects experiencing TEAEs leading to discontinuation of study treatment
- A listing of subjects experiencing TEAEs leading to withdrawal from study
- A listing of deaths

4.5.3 Clinical Laboratory Data

The following laboratory safety assessments will be conducted:

- Hematology: complete blood count (CBC) including red blood cell count (RBCs), white blood cell counts (WBCs) with differentials (neutrophils, lymphocytes, monocytes, eosinophils, and basophils), hemoglobin, hematocrit, mean corpuscular volume (MCV), mean corpuscular hemoglobin (MCH), and mean corpuscular hemoglobin concentration (MCHC).
- Serum chemistry: albumin, alkaline phosphatase, alanine aminotransferase (ALT), aspartate aminotransferase (AST), blood urea nitrogen (BUN), calcium, chloride, carbon dioxide, creatinine, creatine kinase, direct bilirubin, gamma-glutamyl transpeptidase (GGT), glucose, HbA1c, lactate dehydrogenase (LDH), magnesium, phosphorus, potassium, sodium, total cholesterol, total bilirubin, high-density lipoproteins, low-density lipoproteins, triglycerides, total protein, and uric acid
- Urinalysis: including determination of the presence of urine protein, glucose, ketones, occult blood, and WBCs by dipstick, with microscopic examination if indicated

4.5.3.1 Quantitative Analyses

Hematology, serum chemistry, and urinalysis will be summarized by treatment group and visit. Descriptive statistics will be presented at each visit by treatment group, including number of subjects, mean, standard deviation, median, 25%, 75% quartiles, minimum, and maximum values.

Changes from baseline in quantitative laboratory values will be summarized using descriptive statistics by treatment group and visit. Plots of mean values by visits will be presented for numeric laboratory parameters, except for mean corpuscular volume (MCV), mean corpuscular hemoglobin (MCH), and mean corpuscular hemoglobin concentration (MCHC).

Individual subject listings of clinical laboratory parameters at each visit will be provided. Values for hematology, serum chemistry, and urinalysis values outside the central laboratory reference ranges will be flagged on the individual subject data listings.

Visit windows for by visit summaries

For laboratory by visit summaries, the analysis visit is defined by visit windows in the table below. If there is more than 1 value in the same analysis visit window for a certain parameter for a subject, then the closest record to the target visit day will be used for the by visit analysis. If there are 2 values in the same analysis visit window with the same distance from the target visit day for a certain parameter for a subject, then the record with the later date will be used for the by visit analysis. If there are 2 values on the same day for a certain parameter for a subject, then the record with the later time will be used for the by visit analysis.

Table 6: Visit Windows for Laboratory

Analysis visit	Target visit day	Analysis visit window
Baseline	1	Most recent non-missing pre-dose value
Week 1	8	[2, 10]
Week 2	15	[11, 21]
Week 4	29	[22, 42]
Week 8	57	[43, 70]
Week 12	85	[71, one day before start of safety follow-up]
Safety follow-up	Safety follow-up	[start of safety follow up, the end of study]

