Protocol Activity	Day 1 ¹	Week 1/ Day 8 ²	Week 2/ Day 15 ^{1,2}	Week 4/ Day 29 ²	Week 6/ Day 43 ^{1,2}	Week 8/ Day 57 ²	Week 10/ Day 71 ²	Week 12/ Day 85 ^{1,2} /ET ³	14 Days After Last Dose ²	
Vital Signs (temperature, supine blood pressure, pulse rate, respiratory rate) ⁶	X	X	X	X	X	X	X	X		
Laboratory Tests										
Urine Drug and Alcohol Test ⁶	X		X		X			X		
Urine Pregnancy Test ^{6, 11}	X			X		X		X	X	
Clinical Safety Laboratory Tests (hematology, blood chemistry, and urinalysis) ⁶	X	X	X	X		X		X	X	
Antipsychotic Blood Sampling	X							X		
Subject/Informant-Reported Outcomes										
Assessments										
MCCB ¹⁵	X		X		X			X		

CONFIDENTIAL

The information contained herein may not be used, disclosed, or published without the written consent of Biogen MA Inc.

Study Phase:	Baseline	Treatment								SFU
Protocol Activity	Day 1 ¹	Week 1/ Day 8 ²	Week 2/ Day 15 ^{1,2}	Week 4/ Day 29 ²	Week 6/ Day 43 ^{1,2}	Week 8/ Day 57 ²	Week 10/ Day 71 ²	Week 12/ Day 85 ^{1,2} /ET ³	14 Days After Last Dose ²	
SCI-PANSS ^{15, 16}	X		X		X			X		
UPSA-Bi ¹⁵	X							X		
SCoRS ^{15, 16}	X							X		
CGI-S ^{15, 17}	X				X			X		
CGI-I ^{15, 17}					X			X		
Dispense Study Treatment ¹⁸	X	X	X	X	X	X	X			
Monitor Dosing Compliance	X	X	X	X	X	X	X	X		
Study Treatment Administration	Oral dosing BID from Day 1 through Day 85-----									
Adverse Event Recording	X -----									
Serious Adverse Event Reporting	X -----									
Concomitant Therapy and Procedures Recording ⁶	X -----									

AE = adverse event; [REDACTED]; CGI-I = Clinical Global Impression–Improvement; CGI-S = Clinical Global Impression–Severity; C-SSRS = Columbia Suicide Severity Rating Scale; ECG = electrocardiogram; [REDACTED]; ET = Early Termination; h = hours; [REDACTED]; MCCB = MATRICS Consensus Cognitive Battery; PK = pharmacokinetic; SAE = serious adverse event; SARA = Scale for the Assessment and Rating of Ataxia; SCI-PANSS = Structured Clinical Interview for Positive and Negative Syndrome Scale; SCoRS = Schizophrenia Cognition Rating Scale; SFU = Safety Follow-Up; [REDACTED]; UPSA-Bi = UCSD (University of California, San Diego) Performance-Based Skills Assessment – Brief, international version.

CONFIDENTIAL

The information contained herein may not be used, disclosed, or published without the written consent of Biogen MA Inc.

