¹ If needed, cognitive behavioral assessments may be completed over 2 consecutive working days for feasibility and subject comfort. The following efficacy assessments should, whenever possible, be completed in the following order: MCCB, [REDACTED] SCI-PANSS, UPSA-Bi, SCoRS, CGI-S, CGI-I.

² The visit window is ± 3 calendar days relative to baseline. The total time between visits is not to exceed 10 calendar days (for Week 2) or 17 calendar days (for all other visits).

³ Week 12 (Day 85/ET) assessments should be completed in the event of early subject withdrawal/early termination (ET).

⁴ The site will review all Screening Visit assessments against the inclusion/exclusion criteria, assess for any changes from screening, and reconfirm eligibility prior to randomization.

⁵ C-SSRS “Since Last Visit” evaluation.

⁶ The following safety assessments should, whenever possible, be completed in this order: C-SSRS, concomitant medications, weight, physical examination, neurological examination, SARA, 12-lead ECG, vital signs, urine drug and alcohol screening, blood/urine specimens.

⁷ See Section 8.3 and the Study Reference Manual for additional information.

⁸ All women of childbearing potential and all men must practice effective contraception during the study. After their last dose of study treatment, men and women must continue with contraception for at least 30 days.

⁹ To be performed predose for all study sites. For Japanese study sites, see Footnote 10 for additional instructions.

¹⁰ **For Japanese study sites only** (items designated with Footnote 10 are for Japanese sites only unless otherwise specified):

- On Day 1, in addition to baseline assessments, a [REDACTED] will be collected (see Table 5 for timing) and additional safety evaluations (AE recording, 12-lead ECG, brief neurological examination, and SARA) will be performed 2-hours postdose. Should any abnormal findings arise during these evaluations, an additional [REDACTED] will be collected. Dosing will be performed under medical supervision, and observation may be extended at the Investigator’s discretion prior to discharge from the site, if necessary, including an overnight stay.
- On Day 8, a [REDACTED] will be collected (see Table 5 for timing), and additional safety assessments 2-hours postdose (AE recording, 12-lead ECG, brief neurological examination, and SARA) will be performed.

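### SAP Tables 6, 9, 10 and 11 end Week 1 at Day 10, but the protocol allows the Week 1 visit up to Day 11, so an on-schedule Day 11 safety assessment is labelled Week 2

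*SAP*

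**What the plan says.** Protocol Section 5, Table 4, places Week 1 at Day 8 and Week 2 at Day 15. Footnote 2, attached to both columns, reads "The visit window is ± 3 calendar days relative to baseline". It also limits the gap between visits to 10 days for Week 2 and 17 days for the other visits. Safety laboratory tests and vital signs are marked at both Week 1 and Week 2 for all sites. The Week 1 brief examination and SARA carry footnote 10, which restricts them to Japanese sites.

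SAP Section 4.5.3.1 says of laboratory data: "For laboratory by visit summaries, the analysis visit is defined by visit windows in the table below". Table 6 then gives Week 1 as [2, 10] and Week 2 as [11, 21]. If one window holds several values, "then the closest record to the target visit day will be used for the by visit analysis"; if two are equally close, "then the record with the later date will be used for the by visit analysis".

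SAP Section 4.5.4 says "For vital sign by visit summaries, the analysis visit should be defined using window in the table below". Table 9 has the same two windows, and the section has the same closest-record and later-if-tied rules.

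Tables 10 (brief physical and neurological examination, Section 4.5.6) and 11 (SARA, Section 4.5.7) give Week 1 as [2, 10] and Week 2 as [11, 28]. Neither section says which record to use when a window holds more than one.

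**The concern.** An analysis window should contain every day on which the protocol allows the visit. Here the last permitted Week 1 day lies outside the Week 1 window and inside the Week 2 window. A site that follows the protocol exactly can therefore produce a Week 1 result that the SAP treats as Week 2.

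For scheduled laboratory tests and vital signs, Week 1 is the first visit after dosing starts. By-visit values, changes from baseline and the laboratory mean plots at that visit would omit valid observations. If the Week 2 visit is missed, a result from about ten days of treatment would appear under Week 2.

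**Working it through.** **1. Where should Week 1 end?** Two derivations, with targets and tolerance from protocol Table 4:

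- Target plus tolerance: 8 + 3 = Day 11. The protocol window for Week 1 is Days 5-11, and for Week 2 it is 15 ± 3 = Days 12-18.
- Midpoint of the targets: (8 + 15)/2 = 11.5, so the last day nearer to Week 1 is Day 11 (|11 − 8| = 3; |11 − 15| = 4).

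Neither gives the Day 10 printed in the SAP. The protocol's caps on time between visits do not rule out Day 11: it is 10 days after Day 1, and a Week 2 visit on Days 12-18 follows it by 1 to 7 days.

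**2. Does Day 10 follow the SAP's own pattern?** Every other boundary between two scheduled treatment visits in the safety tables lies at the midpoint of the targets, with a tied day going to the later visit.

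| Table | Midpoints | Later window starts at |
|---|---|---|
| 6 | 22, 43, 71 | 22, 43, 71 |
| 9 (after Week 2) | 22, 36, 50, 64, 78 | 22, 36, 50, 64, 78 |
| 10 (Week 2/6) | 29 | 29 |
| 11 (after Week 2) | 29, 64 | 29, 64 |
| 12 | 22, 36, 50, 71 | 22, 36, 50, 71 |
| 6, 9, 10, 11 (Week 1/2) | 11.5 | 11 (the pattern gives 12) |

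**3. What happens to a Day 11 value in Tables 6 and 9?** It falls in the Week 2 window at distance 4 from Day 15.

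| Actual Week 2 visit | Distance from Day 15 | Record used as Week 2 |
|---|---|---|
| Days 12-18 (on schedule) | 0-3 | Week 2 visit; Day 11 value dropped |
| Day 19 | 4 (tie) | Week 2 visit, as the later record |
| Days 20-21 | 5-6 | Day 11 value; true Week 2 value dropped |
| Day 22 or later, or missed | outside window | Day 11 value |

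Week 1 is blank in every row unless another record falls on Days 2-10.

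There are 7 × 7 = 49 combinations of Week 1 on Days 5-11 with Week 2 on Days 12-18. (Six of them exceed the 10-day cap, none with Week 1 on Day 11.) Under the current windows, the 7 combinations with Week 1 on Day 11 all leave Week 1 empty and drop the value. With Week 1 ending at Day 11 and Week 2 starting at Day 12, none of the 49 is mislabelled or dropped.

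**4. How many subjects?** The documents give no distribution of visit days, so these are assumptions. For scatter around Day 8, give each offset d = −3, …, 3 a weight of exp(−d²/2σ²). The share on Day 11 is the weight at d = 3 divided by the sum of all seven.

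- SD 1: 0.0111/2.506 = 0.4%
- SD 1.5: 0.1353/3.694 = 3.7%
- SD 2: 0.3247/4.627 = 7.0%
- Even spread: 1/7 = 14.3%

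If all 219 planned subjects attended Week 1, these would be about 1, 8, 15 and 31 subjects for laboratory tests and vital signs. No count is possible for Tables 10 and 11, because the number of subjects at Japanese sites is not given.

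**The case against.** The strongest case against acting is that very little depends on this. Most of it stands.

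- *No result leaves the record.* Laboratory values stay in the individual listings. The laboratory shift, markedly abnormal and liver-function counts take post-baseline values without reference to the analysis visit, and the vital-sign outlier criteria are not tied to one either. What changes is descriptive by-visit output, with no hypothesis test.
- *Nothing suggests a difference between arms.* The trial is blinded, and the documents give no reason why Day 11 visits would be commoner in one group.
- *Safety decisions about subjects do not use these windows.* The Japan Day 8 review (protocol Section 14.3) uses the subject's available data for Days 1-8, and the IDMC (Section 19.2.1) reviews AE listings and laboratory results.
- *Visits probably cluster at the scheduled day.* If so, the lower shares are the more likely ones.

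This limits the importance of the point but does not remove the discrepancy. The SAP gives no reason for Day 10, and followed literally it puts a compliant assessment under the wrong visit.

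A reader might also infer more than the documents support:

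- *That Day 11 values are discarded in all four tables.* Sections 4.5.6 and 4.5.7 state no closest-record rule, so only relabelling can be shown for Tables 10 and 11.
- *That Week 1 is the first on-drug look for every affected assessment.* This holds for scheduled laboratory tests and vital signs. At Japanese sites the brief neurological examination and SARA are already done 2 hours after the first dose on Day 1.
- *That this is the only gap in the safety windows.* Table 12 has no Week 1 row, so the Japan-only Day 8 ECG falls in the Week 2 window [2, 21]. That is a separate matter.

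**Conclusion.** The SAP is wrong on this point, and the consequence is minor. In Tables 6, 9, 10 and 11 the Week 1 window excludes Day 11, which the protocol permits and which is nearer to the Week 1 target than to the Week 2 target. In the laboratory and vital-sign by-visit summaries an on-schedule Week 2 visit always displaces the Day 11 value. In Tables 10 and 11 the value is relabelled, and what follows is not specified.

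The day arithmetic needs no assumption. The size does: under 1% of Week 1 visits with SD 1 day, about 4-7% with SD 1.5-2 days, and about 14% with an even spread over Days 5-11. The even spread is the top of this range, and the figure of about 31 of 219 depends entirely on it and on full Week 1 attendance. It should not be read as an expected loss. A habit of late visits could give a larger share, but the documents offer no evidence either way.

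The primary endpoint, the other efficacy analyses and the sample size are not affected; the efficacy windows in Tables 2 to 4 have no Week 1 row.

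**What to change.** Set Week 1 to [2, 11] in Tables 6, 9, 10 and 11. Set Week 2 to [12, 21] in Tables 6 and 9 and to [12, 28] in Tables 10 and 11. That is two cells in each of four tables, with no change to data collection or to any other boundary. No downside was found: the new boundary agrees with both the protocol tolerance and the SAP's own midpoint pattern. Making the change before summaries are produced avoids a post hoc adjustment.

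Separately, state how the Japan-only Day 8 ECG is to be summarized, since Table 12 has no Week 1 row. The window change above does not deal with it.
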